14.2.4. Pharmacodynamic Data

The primary analysis population for pharmacodynamic data will be the Per Protocol Set. The secondary analysis population will be the Full Analysis Set.

Pharmacodynamic parameters consist of the following:

- Muscle assessments: Muscle volume and intramuscular fat fraction of TA or BB by MRI
- Biomarkers: including, but not limited to, serum C-terminal collagen crosslinks (CTX)

Part 1

Individual pharmacodynamic data (e.g., total muscle volume, contractile muscle volume, intramuscular fat fraction, and biomarker data) will be listed. For individual pharmacodynamic data that are measured on the left and right side, the average of the left and right side assessments will also be listed and summarized. Descriptive statistics (raw data and change from baseline [percent and absolute change]) will be provided by cohort and scheduled time where baseline is defined to be the last non-missing assessment done prior to first dose.

For the percent change in total muscle volume at 6-months from baseline, a mixed model will be fitted using the data from Part 1 as well as the data from the double-blind component of Part 2 of studies A083-02 and A083-03 and the loading dose treatment effect will be assessed. Baseline is defined to be the last non-missing value prior to first dose of study medication. The least squares mean difference for each loading dose regimen (q4w and q3w) vs. placebo and corresponding 90% confidence interval will be provided where placebo subjects come from the double-blind component of Part 2 of A083-02 and A083-03. This will also be provided by cohort. If data from the 6-month (Day 169) visit are missing, the missing data mechanism will be investigated and an appropriate method for handling the missing data will be applied. Sensitivity analyses will also be performed.

For contractile muscle volume and intramuscular fat fraction, similar analyses as described above for total muscle volume will be provided. For biomarker data (e.g., IGF-1 and CTX), raw data and changes from baseline (percent and absolute change) will be summarized by cohort and scheduled time.

Additional analyses may be performed as appropriate.

Part 2

Individual pharmacodynamic parameter data will be listed. Descriptive statistics will be provided by cohort, treatment regimen and scheduled time for raw data and changes from baseline.

The primary pharmacodynamic variable will be the difference in mean percent change in total muscle volume (average of left and right side) for the first 6 months of the maintenance phase (Day 169) from the total muscle volume (average of left and right sides) at the start of the maintenance phase (or equivalently the end of the loading phase). An mixed model will be fitted to the data and a non-inferiority analysis will be performed using a non-inferiority margin of -5. The non-inferiority analysis will be done for each maintenance dose regimen (q4w and q8w). The lower bound of the one-sided 95% confidence interval will be used to assess non-inferiority. If data from the 6-month (Day 169) visit are missing, the missing data mechanism will be investigated and an appropriate method for handling the missing data will be applied. Sensitivity analyses will also be performed. In addition, using the same mixed model, the percent change in total muscle volume for the first 6 months of the maintenance phase (Day 169) from the start of the maintenance phase (or equivalently the end of the loading phase) will be compared between the two dosing regimens (q8w vs q4w).

Secondary MRI pharmacodynamic variables include the difference in mean percent change for contractile muscle volume (average of left and right sides) as well intramuscular fat fraction (average of left and right sides) at the end of the first 6 months of the maintenance phase (Day 169, q4w or q8w) from the start of the maintenance phase (or equivalently the end of the loading phase). Secondary pharmacodynamic variables also include the percent and/or absolute (raw) change in biomarker variables such as CTX at the end of the first 6 months of the maintenance phase (Day 169). For each secondary MRI pharmacodynamic variable, an mixed model will be fitted to the data and least square estimates of the mean difference and corresponding 90% confidence interval will be provided for each maintenance dose regimen. If data from the 6-month (Day 169) visit are missing, the missing data mechanism will be investigated and an appropriate method for handling the missing data will be applied. Sensitivity analyses will also be performed.

For biomarker data, a mixed model will be fitted and least-square estimates of the mean percent and/or absolute change from baseline for the first 6 months of the maintenance phase along with the corresponding 90% confidence interval will be provided for each maintenance dose regimen. If data from the 6-month (Day 169) visit are missing, the missing data mechanism will be investigated and an appropriate method for handling the missing data will be applied. Sensitivity analyses will also be performed.

Least square estimates of the mean percent or absolute change from the start of the maintenance phase (or equivalently the end of the loading phase) for other scheduled times during the maintenance phase along with the corresponding 90% confidence interval may be provided as appropriate.

Additional analyses may be performed as appropriate.

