Safety: Unless otherwise specified, safety data will be summarized, by cohort and overall, using descriptive statistics; individual safety data will be listed. AEs will be coded using the current version of the Medical Dictionary for Regulatory Activities and incidence of treatment-emergent AEs will be presented by system organ class and preferred term. AE incidence rates will be described by cohort with and without regard to causality. The frequency of occurrence of overall toxicity, categorized by toxicity grades (NCI-CTCAE, current version), will be summarized. Change from baseline in clinical laboratory parameters, ECG, and vital signs will be summarized across time. Shift tables will be presented for selected laboratory parameters and vital signs. Physical examination results will be presented in listings.

Pharmacodynamics: Individual PD data (e.g., total muscle volume, contractile muscle volume, intramuscular fat fraction, and biomarker data) will be listed. For individual PD data that are measured bilaterally (e.g., MRI), the average of the left and right side assessments will also be listed and summarized. Descriptive statistics (raw data and change from baseline [percent and

absolute change]) will be provided by cohort and scheduled time where baseline is defined to be the last non-missing assessment done prior to first dose.

For total muscle volume, contractile muscle volume, and intramuscular fat fraction, a mixed model will be fitted to the data and the least squares estimate of the mean difference in the percent change from baseline at 6 months post first dose under the q4w regimen of ACE-083 versus placebo will be determined for each cohort with the corresponding 90% confidence interval, where placebo refers to data from the double-blind component of Part 2 of either study A083-02 or A083-03. This will be compared with the findings from Part 2 of studies A083-02 and A083-03 for the mean difference in the percent change from baseline under the q3w regimen vs placebo.

For biomarker data (e.g. CTX), raw data and changes from baseline (percent and absolute change) will be summarized by cohort and scheduled time.

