Patients with CMT typically present with both motor and sensory nerve symptoms, including distal leg weakness, foot deformities (pes cavus, hammer toes), and sensory deficits. Involvement of the hands may also follow as the disease progresses. Weakness in the lower leg manifests as foot drop, and patients have difficulty lifting their toes while walking. As this weakness progresses, patients lose mobility and are at increased risk for falls and injury.

There is a high unmet medical need for drug therapy options in both CMT and FSHD. Although some clinical and pharmacological trials have been performed in both patient populations, the results have not been encouraging, and there is currently no approved therapy available for either condition. To date, treatment for both FSHD and CMT has been restricted to symptomatic interventions. Patients will commonly wear braces and/or use assistive devices such as canes and walkers to preserve mobility, but each of these orthopedic interventions is associated with practical as well as social limitations. Surgery can successfully treat some, but not all, foot deformities (in CMT) and foot drop (in CMT and FSHD), but surgical intervention is not appropriate for every case. Exercise is recommended for some patients; however, the safety of exercise, as well as the appropriate regimen of exercise, must be established for each individual patient. Although the safety of exercise is recommended for some patients; however, the safety of exercise, as well as the appropriate regimen of exercise, must be established for each individual patient.

In our Phase 1 study, local injection of ACE-083 into the tibialis anterior (TA) of healthy volunteers led to a dose-dependent increase in TA muscle volume. In Phase 2 Studies A083-02 and A083-03, subjects received 150 to 240 mg/muscle, unilaterally or bilaterally q3w for 3 months (5 doses, Part 1) or 240 mg/muscle bilaterally for 12 months (17 doses, Part 2). Preliminary data for Part 1 of the study indicated that the study drug was well tolerated and produced significant muscle volume increases that were maintained for up to 8 weeks following the last dose.

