7. STUDY DESIGN

7.1. Overview of Study Design

This is an open-label, multicenter, phase 2 extension study to evaluate the safety, tolerability, PD, efficacy, and PK of ACE-083 in patients with FSHD previously enrolled in Study A083-02 and patients with CMT1 and CMTX previously enrolled in Study A083-03. This study will be conducted in two Parts: Part 1, consisting of a loading phase of 6 months, and Part 2, consisting of a maintenance phase of 24 months. Subjects who enroll in this study without interruption of treatment following the previous study will enroll directly into Part 2 of this study.

Part 1 is a non-randomized, open-label, loading phase in which subjects will receive bilateral injections of 240 mg/muscle ACE-083 every 4 weeks. Part 1 will include subjects previously treated in Part 1 of Studies A083-02 and A083-03 after a washout period of at least 3 months. Upon completion of this 6-month loading phase, these subjects will then rollover into Part 2 of this study, which is the maintenance phase.

Subjects who complete Part 2 of study A083-02 or A083-03 will enroll directly into Part 2 of this study without interruption. The end-of-treatment visit in the previous study will coincide with the Day 1 visit of this study. Part 2 is an open-label maintenance phase study in which subjects will be randomized to receive bilateral injections of 240 mg/muscle ACE-083 either every 4 weeks or every 8 weeks. A schematic diagram of subject enrollment and disposition is shown in Figure 1.

Duration of Treatment

For subjects enrolled in Part 1 and Part 2 of this study, study duration will be approximately 33 months, including a screening period of up to 1 month, the 6-month Part 1 loading phase, the Part 2 maintenance phase of 24 months, and a 2-month follow-up period.

For subjects who enroll directly into Part 2 of this study from Part 2 of Study A083-02 or A083-03, study duration will be approximately 26 months, including a maintenance phase of 24 months and a 2-month follow-up period. These subjects will sign the Informed Consent Form (ICF) for this study at the end-of-treatment visit for Study A083-02 or Study A083-03 (i.e., Day 1 of this study).

If a subject has a positive anti-drug antibody (ADA) result at the last scheduled follow-up visit, the subject may be asked to return for additional ADA testing approximately every 3 months, until a negative result is obtained or the titer is no longer increasing.

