Part 1 (non-randomized, open-label, loading phase with subjects from A083-02 Part 1 and A083-03 part 1)

Part 1 will consist of 3 cohorts of up to 18 subjects each. In this loading phase, 240 mg/muscle ACE-083 will be administered bilaterally q4w for 6 doses (6 months) into either the TA muscle or BB muscle, depending on the muscle injected in the previous study; subjects may not switch muscle cohort upon enrollment in this study. Subjects in each cohort will be enrolled in a screening period of up to 4 weeks before beginning treatment.

Subjects enrolled in Cohorts 1a and 1b will have completed the 3-month, dose escalation, non-randomized, open-label Part 1 of Study A083-02. As part of that study, these subjects will have

Revision: 00 previously received injections of up to 240 mg/muscle ACE-083, either unilaterally or bilaterally, q3w for up to 5 doses.

Subjects enrolled in Cohort 1c, will have completed the 3-month, dose escalation, non-randomized, open-label Part 1 of Study A083-03. These subjects will have previously received up to 240 mg/muscle ACE-083 bilaterally by injection into the TA every q3w for up to 5 doses.

Part 2 (randomized, open-label rollover maintenance phase, with subjects from Part 1 A083-04 and A083-02 part 2 and A083-03 part 2)

Part 2 will consist of 6 additional cohorts. Cohorts 2a, 2b, and 2c will receive 240 mg/muscle ACE-083 q4w, and Cohorts 3a, 3b, and 3c will receive 240 mg/muscle ACE-083 q8w. Cohorts are separated and randomized based upon disease (FSHD or CMT) and target muscle (BB or TA).

Subjects who complete Part 1 (loading phase), will immediately rollover into Part 2 (open-label maintenance phase) treatment with ACE-083. The subjects will be randomized into treatment groups to receive 240 mg/muscle ACE-083 bilaterally either q4w or q8w.

Subjects who completed Part 2 of Study A083-02 or Part 2 of Study A083-03 will directly enter into Part 2 (open-label maintenance phase) of this study and will be randomized to receive 240 mg/muscle either q4w or q8w. The first study visit of this study will coincide with the end-of-treatment visit of the previous study (either A083-02 or A083-03).

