8. STUDY POPULATION

8.1. Inclusion Criteria

Subjects are eligible to be included in the study only if they meet all of the following criteria at screening:

Inclusion Criteria:

- 1. Completion of treatment with study drug per protocol and completion of the end of treatment (ET) visit in Study A083-02 or Study A083-03.
- 2. Females of childbearing potential (defined as sexually mature women who have not undergone hysterectomy or bilateral oophorectomy, or are not naturally postmenopausal ≥ 24 consecutive months) must have negative urine pregnancy test prior to enrollment and use highly effective birth control methods (abstinence, oral contraceptives, barrier method with spermicide, or surgical sterilization) during study participation and for 8 weeks following the last dose of ACE-083. Hormonal birth control use must be stable for at least 14 days prior to Day 1. Males must agree to use a condom during any sexual contact with females of childbearing potential while participating in the study and for 8 weeks following the last dose of ACE-083, even if they have undergone a vasectomy. Subjects must be counseled about contraception prior to the first dose of ACE-083 and every three months thereafter during the study.
- 3. Ability to adhere to the study visit schedule/procedures and to understand and comply with protocol requirements
- 4. Signed written informed consent

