8.2. Exclusion Criteria

Subjects will be excluded from study enrollment if they meet any of the following criteria at screening:

- 1. Current/active malignancy (e.g., remission less than 5 years' duration), with the exception of fully excised or treated basal cell carcinoma, cervical carcinoma in-situ, or ≤ 2 squamous cell carcinomas of the skin
- 2. Co-morbidities, including symptomatic cardiopulmonary disease, significant orthopedic or neuropathic pain, or other conditions that, in the opinion of the investigator, would limit a subject's ability to complete strength and/or functional assessments
- 3. Type 1 or type 2 diabetes mellitus
- 4. Thyroid disorder unless condition is stable with no change in treatment for at least 4 weeks before the first dose and no expected change for duration of study
- 5. Renal impairment (serum creatinine ≥ 2 times the upper limit of normal [ULN])
- 6. Aspartate transaminase (AST) and/or alanine transaminase (ALT) \geq 3 times ULN
- 7. Increased risk of bleeding (i.e., due to hemophilia, platelet disorders, or use of any anticoagulation/platelet modifying therapies up to 2 weeks prior to Study Day 1 and for duration of study; single agent low dose aspirin [≤ 100 mg daily] is permitted)

- 8. Severe deformity or ankle fixation that would sufficiently limit passive range of motion to affect functional assessments (TA patients only)
- 9. Major surgery within 4 weeks prior to Study Day 1
- 10. Chronic pharmacologic doses of systemic corticosteroids (≥ 2 weeks) within 4 weeks before Study Day 1 and for duration of study; intra-articular/topical/inhaled/intranasal physiologic doses of systemic corticosteroids are permitted
- 11. Androgens, growth hormone, insulin or oral hormone replacement therapy within 6 months before Study Day 1 and for duration of study; topical physiologic androgen replacement is permitted
- 12. Any change in medications potentially affecting muscle strength or function within 4 weeks of Study Day 1 and for duration of study (e.g., creatinine, CoQ10, systemic beta-adrenergic agonists)
- 13. Previous exposure to any other investigational agent (not including ACE-083) potentially affecting muscle volume, muscle strength, or muscle or nerve function within 5 half-lives of last dose plus an additional 8-week washout period (or 12 weeks prior to Study Day 1 if half-life is unknown)

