APPENDIX 1. SCHEDULE OF EVENTS

Table 8: Schedule of Events for Part 1: Loading Phase

	Screening	Part 1: Loading Phase*										
Dose	-	L1	L2	L3	L4	L5	L6					
Planned Day	-28 to -1	1	29 ± 3d	57 ± 3d	85 ± 3d	113 ± 3d	141 ± 3d					
Informed Consent	X											
Inclusion/exclusion criteria	X											
Urine pregnancy test		X		X		X						
Medical History	X											
MMT assessment (MRC)	X	X			X							
Full Physical examination ²	X											
Limited Physical examination ²		X			X							
Injection site examination		X	X	X	X	X	X					
Vital signs ³	X	X	X	X	X	X	X					
Hematology	X	X		X		X						
Chemistry	X	X		X		X						
Urinalysis		X		X		X						
Biomarkers		X			X							
Anti-drug antibody	X	X		X		X						
Serum PK ⁶		0,1, 2, 4, 24 h			0,1, 2, 4, 24 h	X	X					
ECG (12 lead) ⁷	X	X			X							
Bilateral MRI ⁴		X			X							
10MWR, 6MWT, 100mTT (all TA subjects); 4-stair climb (FSHD TA subjects); PUL (FSHD BB subjects) ⁵	X	X			X							
QMT assessment (MVIC by hand-held dynamometer)	X	X			X							
FSHD-HI or CMT-HI	X	X			X							
Monitoring of concomitant medications	X	X	X	X	X	X	X					
Monitoring of adverse events	X	X	X	X	X	X	X					
Study drug administration ¹		X	X	X	X	X	X					

^{*}The L before the Dose in this table denotes that these doses occur in the Loading Phase.

¹ Study procedures must be done prior to administration of study drug. Reference the Study Manual for the order of study procedures. All visit-day windows should be considered relative to the date of the previous dose of ACE-083. Actual visit days (e.g. Day 29, Day 57) may be different than planned due to windows on visits and dosing delays.

² Full physical examination during the screening period; limited physical examination for Days 1, 85.

³ Vital signs (weight, heart rate, systolic and diastolic blood pressure) must be taken prior to administration of study drug on dosing days

⁴MRI should be completed within 5 days prior to scheduled dose administration, with the exception of the Day 1 MRI, which may be completed within 14 days prior to the Day 1 visit. If performed on the same day as study drug administration, the subject should receive the MRI first.

⁵ These function tests may be performed within 3 days prior to Day 1 visit.

⁶ PK samples on dosing day have a ±15 minute window with the exception of the 24 h time point, which has a ± 2 window. Pre-dose samples may be collected up to 4 h prior to dosing.

 $^{^{7}}$ ECG to be conducted ± 1 hour of the 4h PK sample

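### Could volume left over from the parent study raise the Part 1 baseline enough to require a change to the q4w analysis?

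*Protocol*

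**What the plan says.** Section 7.1 describes who enters Part 1: "Part 1 will include subjects previously treated in Part 1 of Studies A083-02 and A083-03 after a washout period of at least 3 months". The FSHD subjects (Cohorts 1a and 1b) had "previously received injections of up to 240 mg/muscle ACE-083, either unilaterally or bilaterally, q3w for up to 5 doses". The CMT subjects (Cohort 1c) had up to 5 q3w doses on both sides. Subjects stay with the muscle injected before.

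Section 14.2.4 (Part 1) takes the last value before the first dose as baseline. Section 14.2.3 uses the same definition and notes that this should in theory be the Day 1 pre-dose value. Table 8 schedules the baseline MRI at Day 1, and its footnote 4 allows some latitude: "with the exception of the Day 1 MRI, which may be completed within 14 days prior to the Day 1 visit".

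The analysis is then as follows: "The least squares mean difference for each loading dose regimen (q4w and q3w) vs. placebo and corresponding 90% confidence interval will be provided". The placebo subjects come from the double-blind component of Part 2 of the parent studies. The synopsis adds, about the q4w result: "This will be compared with the findings from Part 2 of studies A083-02 and A083-03", meaning the q3w result there.

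On persistence, section 5.2 reports that the drug "produced significant muscle volume increases that were maintained for up to 8 weeks following the last dose". Section 7.2 says the same. Neither says when volume returns to its pre-treatment level.

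Section 8 does not repeat the washout. Inclusion criterion 1 asks for "Completion of treatment with study drug per protocol and completion of the end of treatment (ET) visit in Study A083-02 or Study A083-03". Exclusion criterion 13 has a washout for other agents but leaves out the study drug: "Previous exposure to any other investigational agent (not including ACE-083) potentially affecting muscle volume".

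**The concern.** A percent change is only as clean as its denominator. If a muscle is still enlarged from the parent study when the Day 1 scan is taken, the gain measured from that scan can be too small. The placebo and q3w results beside it would not be reduced in the same way, provided the parent Part 2 subjects had no earlier ACE-083. The protocol does not state this, so it is an assumption.

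The safeguard also looks thin. The washout appears in a design paragraph and not in the eligibility list, the synopsis or the schedule of events. It names no event from which it is counted, and the scan may be taken two weeks early. Percent change in muscle volume is a listed primary endpoint, so an understated q4w loading effect would matter to anyone choosing between loading schedules.

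**Working it through.** The protocol gives no figure for the Part 1 effect or for its precision, so there is none to reproduce. Two things can be checked: the timing, and how a residual would pass into the estimate.

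**Timing.** Inputs: washout of at least 3 months (7.1); gains maintained for up to 8 weeks (5.2, 7.2); MRI up to 14 days before Day 1 (Table 8, footnote 4). Three months is 12 weeks by the protocol's own usage, since it calls Day 169 six months and 168/7 = 24 weeks. By the calendar it is 13 weeks.

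- Washout from last dose to Day 1, earliest permitted scan: 12 − 2 = 10 or 13 − 2 = 11 weeks after the last dose. That is 2 to 3 weeks past the 8-week point.
- Washout from last dose, complete by screening: sections 8.1 and 8.2 apply eligibility at screening, and 12.1 requires consent before any study procedure. The scan then falls at 12 to 13 weeks or later, at least 4 to 5 weeks past the 8-week point.
- Washout from a visit 8 weeks after the last dose (an assumed example) to Day 1, earliest scan: 8 + 12 − 2 = 18 or 8 + 13 − 2 = 19 weeks.

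The first case is the worst that 7.1 permits, and it needs the minimum washout, the latest end event and the earliest scan together. The last dose is the earliest plausible start. The missing start event therefore cannot bring the scan closer to that dose than the first case does.

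**Effect of a residual.** Let g be the true gain over the untreated volume and d the Day 1 volume above it. The protocol gives neither, so the values below are assumptions.

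- If re-treated muscle reaches the same end volume, the measured gain is (1 + g)/(1 + d) − 1 and the shortfall is (1 + g)d/(1 + d). With g = 12% and d = 3%: 1.12/1.03 − 1 = 8.74%, a shortfall of 3.26 points. With d = 1%, the shortfall is 1.07, 1.11 and 1.15 points for g = 8%, 12% and 16%.
- If only one side was dosed before and the sides are equal in volume, d is halved in the left-right average. With g = 12% and d = 1%: 1.12 × 0.005/1.005 = 0.56 point.
- If re-treatment adds the same percentage to the current volume, the measured gain is (1 + d)(1 + g)/(1 + d) − 1 = g. The shortfall is 0 for any d.
- If nothing remains at Day 1, d = 0 and the shortfall is 0.

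For scale, take the SD of 9 from section 14.3 and a full cohort of 18. The 90% half-width of one cohort mean is 1.645 × 9/√18 = 3.5 points, or 3.7 with the t quantile. The interval for a difference from placebo would be wider.

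These figures convert an assumed residual into points. They do not show that a residual exists.

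**Section 8 beside 7.1.** The same eligibility list serves subjects who enter Part 2 directly without a break in treatment (7.1). Exclusion criterion 13 has to exempt ACE-083 for them, and a general ACE-083 washout there would shut them out. Section 8 is therefore silent on the Part 1 washout but does not contradict it, and 7.1 remains binding protocol text.

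**The case for a change.** The strongest case for a change is this. The protocol recognises carry-over as a threat to this endpoint, because it imposes a washout for other agents that affect muscle volume. It gives no evidence that volume has returned to its starting level by 3 months. A site working from section 8 alone could enter a subject early. Model covariates in the SAP would not repair eligibility text. The remedy looks cheap: repeat the washout in section 8, tabulate Day 1 volume against the parent pre-treatment scan and, if a residual shows, rerun the model from that earlier baseline.

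The facts stand, and a residual is not excluded. The remedies gain little:

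- Repeating the washout with its start and end events would tidy the text. Without a different interval, it leaves the question of a residual where it was.
- The descriptive table changes no estimate. It is ordinary SAP content, and 14.2.4 leaves room for additional analyses. It needs pre-treatment scans by side, and this protocol does not show that an undosed side was scanned in the parent study.
- A rerun made only when a residual is seen depends on the data and has no threshold. Sections 5.2 and 7.1 describe progressive disease and time off drug, so decline could mask a residual. If a 3% residual met an assumed decline of the same size, Day 1 volume would be 1.03 × 0.97 = 0.999 of the parent value. For the same reason the two estimates need not enclose the truth. The second would also include the earlier q3w course: with a 12% Day 1 gain and a 3% residual, it gives 1.03 × 1.12 − 1 = 15.4%.

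**Conclusion.** No change to the plan follows. Read with 7.1, the protocol separates the earlier course from the Part 1 baseline by more than the 8 weeks for which it reports the gain as maintained. The least favourable reading still leaves 2 to 3 weeks beyond that point. Carry-over is possible but not shown. Its size cannot be derived from the protocol and may be 0.

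The Day 1 baseline is a fair choice for the effect of the q4w course in subjects entering this study. The comparison is a non-randomised, cross-study estimate with no test attached, and its readers will know that the subjects were treated before. Section 8's silence on the washout is editorial.

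This rests on two assumptions: that sites follow 7.1, and that the washout is counted from the last parent dose or later. The Part 2 primary pharmacodynamic variable is measured from the start of maintenance and is not affected.
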